5.3 Duration of Therapy

In the absence of treatment delays due to adverse event(s), treatment may continue for up to 18 courses:

5.3.1 On-Study Data Submission Schedule

Pre-treatment, on-study and off-treatment data, as well as subject response data are to be recorded in the electronic data collection screens using the PBTC RDC database. See the Required Data and Timetable for Submission form located on the PBTC-039 protocol and resources webpage for the schedule. For assistance, contact the PBTC Protocol Coordinator,

listed on the cover page of the protocol. An optional roadmap is located on the PBTC-039 protocol and resources webpage.

5.3.2 Off Treatment Criteria

At the discontinuation of treatment, the "Off Treatment Date" is to be recorded in the eCRF and is to be consistent with the reason given for going off treatment. The "Last Treatment Date" is defined as the last date that the patient received protocol based therapy. Date of "off treatment" must be the greatest of the date of last treatment, date of procedure, date of patient assessment, notification of patient/family decision, or decision made by the physician that resulted in the patient being taken off protocol treatment. The reason for discontinuation of treatment must be documented by the attending investigator in the medical record and recorded in the eCRF.

- Disease progression as defined in Section 11.1.3
- Development of a medical or psychiatric illness that in the investigator's judgment renders the patient incapable of further therapy on this protocol.
- Unacceptable toxicity as outlined in sections 6.
- Patient, parent or legal guardian refuses further treatment on this protocol
- Pregnancy or breastfeeding
- Subject is unable to complete the study evaluations/visits
- Patients who develop significant depression and/or suicidal ideations will be taken off treatment.

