5.2 Criteria for Starting Subsequent Courses

A course may be repeated every 6 weeks if the subject has no evidence of progression and has again met laboratory parameters as defined in Section 3.1.11. If a subject does not meet these parameters at the end of the treatment course, then SYLATRON should be held until parameters meet the eligibility criteria. If the next course is delayed >21 days due to failure to meet laboratory parameters of eligibility criteria or drug-related toxicity, the subject should be taken off protocol therapy.

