10 STUDY CALENDAR

Table 2 Standard Clinical and Laboratory Assessments

| | Pre- Therapy | Course 1 | Course 2-9 | Course 10-18 | End of Treatment |
|--|---------------------------|----------------|----------------|---------------------------|---------------------|
| PHYSICAL ASSESSMENTS | | | | | |
| Complete History | X | | | | |
| Interval History | | X ^A | X ^C | $\mathbf{X}^{\mathbf{F}}$ | X |
| Psychiatric History** | X | X ^A | XC | $\mathbf{X}^{\mathbf{F}}$ | X |
| Performance status | X | X ^A | X ^C | $\mathbf{X}^{\mathbf{F}}$ | X |
| Physical including neurologic exam | X | X ^A | X ^C | $\mathbf{X}^{\mathbf{F}}$ | X |
| Visual field evaluation (as feasible) | X | | X ^C | $\mathbf{X}^{\mathbf{F}}$ | |
| Ophthalmology evaluation | X | | X ^C | $\mathbf{X}^{\mathbf{F}}$ | |
| Vital signs | X | X ^A | X ^C | $\mathbf{X}^{\mathbf{F}}$ | X |
| LABORATORY EVALUATION | | | | | |
| CBC (WBC, Hgb, Hct, Platelets, ANC, ALC) | X | X ^A | XC | \mathbf{X}^{F} | X |
| Serum Chemistries (Electrolytes, BUN, Creatinine, SGOT(AST), SGPT(ALT), Total Bilirubin, TSH | X | X ^A | X ^C | X ^F | X |
| Urinalysis for protein (Urine Dip) | X | X ^A | X ^C | X ^F | X |
| Serum or urine pregnancy test (for females of childbearing potential) | X | X ^C | X ^C | X ^F | |
| IMAGING EVALUATION | | | | | |
| Brain MRI with thin cuts through the sella ^D | X | | X^B | $\mathbf{X}^{\mathbf{G}}$ | X |
| OTHER | | | | | |
| Biology Studies (assessment of WNT and MAPK pathway activation) | $\mathbf{X}^{\mathbf{E}}$ | | | | |
| FFPE tumor tissue for PBTC CRB | X^{E} | | | | |
| PBMC for PBTC CRB | X^{E} | | | | |

- Assessments should be done prior to starting course 2, i.e. prior to the 7th injection.
- B Obtain every 12 weeks at time of visit and at time of progression as feasible
- C Obtain every 12 weeks at time of visit
- D See section 9.3 9.3.1
- E See section 9.1.
- F Obtain every 18 weeks at time of visit
- Obtain every 18 weeks at time of visit and at time of progression as feasible

^{*} NOTE: Patients who do not have a Brain MRI performed at or after 9 courses (approximately 12 months) will be considered failures for the purpose of assessing the primary objective according to the statistical design. See section 13.4.1.

** Psychiatric History: patient/family will be queried about mood, depression and suicidal ideations at each study visit. If there are any concerns about significant depression or any suicidal ideation, patient should be referred to Psychiatrist.

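### Suicidal ideation is a mandatory stop, but for a drug injected weekly at home the planned mood checks are 12 and then 18 weeks apart, and the 6-week course gate includes none

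*Combined protocol and SAP*

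**What the plan says.** Section 5.3.2 lists, among the reasons for ending treatment: "Patients who develop significant depression and/or suicidal ideations will be taken off treatment".

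The means of detection is in Section 10. The double-asterisk note to Table 2 says "patient/family will be queried about mood, depression and suicidal ideations at each study visit", and adds: "If there are any concerns about significant depression or any suicidal ideation, patient should be referred to Psychiatrist". The Psychiatric History row is ticked before therapy and at end of treatment. Between those, its timing comes from three footnotes:

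- Course 1: "Assessments should be done prior to starting course 2, i.e. prior to the 7th injection".
- Courses 2-9: "C Obtain every 12 weeks at time of visit".
- Courses 10-18: "F Obtain every 18 weeks at time of visit".

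Section 5.1 sets weekly injections, given by the patient or a parent, for up to 18 six-week courses that follow each other without interruption. Section 5.2 governs each new course: "A course may be repeated every 6 weeks if the subject has no evidence of progression and has again met laboratory parameters". Toxicity enters that section only through the delay rule: "If the next course is delayed >21 days due to failure to meet laboratory parameters of eligibility criteria or drug-related toxicity", the patient leaves protocol therapy. No mood item is named.

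**The concern.** A stop rule protects a patient only once someone knows that its condition has been met. Here the condition is subjective and may not be volunteered, while exposure continues weekly at home. The plan creates a decision point every six weeks but does not put the question there. Between planned queries the rule relies on the patient or family raising the matter unprompted.

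The protocol itself treats the risk as real. Section 7.1 places depression among effects expected in more than 20 of 100 people, and thoughts of suicide or of harming others in the group of 4 to 20 per 100. That list gives neither dose nor population, so the rates may not carry over to children at 1 mcg/kg/week. What is at stake is patient safety. Endpoints, error rates and sample size are not touched.

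**Working it through.** The plan states no figure to reproduce, so the check is a count from the calendar.

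**Inputs.** 18 courses × 6 injections = 108 weekly doses (Section 5.1), placed at weeks 0 to 107. Courses 2-18 start at weeks 6, 12, ..., 102, which is 17 starts. The pre-therapy query is put at week 0. The query before the 7th injection is at week 6. Later queries follow the 12- and 18-week intervals of Table 2. Week 108 is end of treatment and is not counted as on treatment.

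**Anchoring.** Table 2 does not say from which week the intervals run, so three readings were counted:

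- A: 12-week intervals from week 6, 18-week intervals from week 54.
- B: 12-week intervals from week 0, 18-week intervals from week 48.
- C: both counted from week 0, so that the 18-week visits fall at weeks 54, 72 and 90.

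| Reading | On-treatment queries (week) | Number | Starts without query | Gaps in doses, from week 0 |
|---|---|---|---|---|
| A | 6, 18, 30, 42, 54, 72, 90 | 7 | 17 − 7 = 10 | 6, 12, 12, 12, 12, 18, 18, 18 |
| B | 6, 12, 24, 36, 48, 66, 84, 102 | 8 | 17 − 8 = 9 | 6, 6, 12, 12, 12, 18, 18, 18, 6 |
| C | 6, 12, 24, 36, 48, 54, 72, 90 | 8 | 17 − 8 = 9 | 6, 6, 12, 12, 12, 6, 18, 18, 18 |

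Each row of gaps sums to 108.

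**Doses given long after a query.** A 12-dose gap contains 12 − 6 = 6 doses that are six or more weeks after the last query. An 18-dose gap contains 18 − 6 = 12 such doses, and 18 − 12 = 6 that are twelve or more weeks after it.

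- Six or more weeks, A: 4 × 6 + 3 × 12 = 60, and 60/108 = 55.6%.
- Six or more weeks, B and C: 3 × 6 + 3 × 12 = 54, and 54/108 = 50.0%.
- Twelve or more weeks, all readings: 3 × 6 = 18, and 18/108 = 16.7%.

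**With a query at all 17 later course starts.** Every gap is 6 doses, and both counts are 0.

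**Could other planned contacts fill the gaps?** Section 5.1 recommends a call within 72 hours of the first dose, but this precedes the week-6 query and shortens no later gap. The Table 2 note covers every study visit, yet the calendar plans none between the 12- or 18-week visits. The laboratory values needed for Section 5.2 need not bring the patient in, because Section 3.4 allows them to be obtained at an outside certified laboratory.

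**The case against.** The strongest reply is that nothing is inconsistent. Section 5.3.2 states a criterion that applies continuously, and Table 2 states when it is actively looked for. A patient who meets the criterion is already off treatment, so repeating it in Section 5.2 adds no rule. The mood query follows the same schedule as history, examination and blood tests, and the documents give no standard by which 12 or 18 weeks is too long.

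The plan also has other safeguards. Section 3.2.5 excludes severe psychiatric illness, including major depression, and previous suicide attempts. Any concern leads to psychiatric referral. Section 6.3 stops the drug for related grade 3 non-hematologic toxicity and covers persistent grade 2 events. An unscheduled report can trigger the stop at any time. Section 2.2.3 calls this dose well tolerated in children, with intolerable behavioral toxicity at higher doses; the one dose-limiting event in 12 patients was myoclonus. The dosing diary and data-submission forms are held outside the document and could contain between-visit prompts.

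Much of this stands. It is why the point is an improvement and not an error, and why the Section 7.1 rates cannot be turned into expected cases. It is also fair that the 54-60 doses restate the intervals in another unit, and that the upper end needs reading A. Section 9.3.3 schedules imaging from baseline on the same 12-week cycle, which favors a week-0 count and hence 54 doses and 9 starts.

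But none of the safeguards shortens the planned interval. The Section 5.2 condition overlaps Section 5.3.2 in content but not in effect: it makes someone ask before each course. Twelve patients are also thin reassurance. If none of them had a psychiatric dose-limiting event, the one-sided 95% upper bound is still 1 − 0.05^(1/12) = 22%.

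**Conclusion.** The concern holds. Planned surveillance for a mandatory stopping condition leaves gaps of 12 weekly home doses in courses 2-9 and 18 in courses 10-18, under every reading of the calendar. The counts assume 18 courses completed without delay or extra visits; a patient who stops earlier has fewer affected doses.

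The sponsor should make the change because it is cheap and concerns safety. The point is about the interval between planned queries, not the stop rule itself. The number of patients in whom detection would be late cannot be derived. Confidence is medium, because the risk at this dose in children is not quantified in the documents.

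**What to change.** Add a short query about mood, depression and suicidal ideation at each six-week course start, by telephone when no visit is due, through a footnote to the Psychiatric History row of Table 2. In Section 5.2, add as a condition for the next course: *no significant depression or suicidal ideation (see 5.3.2)*. The footnote should say that a positive answer by telephone follows the existing psychiatric referral path.

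The cost is 17 − 8 = 9 to 17 − 7 = 10 short, documented calls per patient who completes 18 courses, plus an amendment for the two text changes. No visits, imaging or laboratory tests are added, and the sample size is unchanged.

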5.4 Off Treatment Duration of Follow Up

Patients who are off protocol therapy must be followed until an "Off Study Criterion" is met (see section 5.6).

- 5.4.1 Patients who have had progression/recurrence will be followed for 30 days after the last dose of SYLATRON or until the resolution of all SYLATRON related toxicities, whichever is longer.
- 5.4.2 Patients who discontinue for reasons other than progression/recurrence of disease should continue to be followed for progression/recurrence, i.e. until they meet the Off Study criteria (below). Follow-up data will be required.
- 5.4.3 Patients removed from study for unacceptable adverse event(s) will be followed until resolution or stabilization of the adverse event and they meet one of the Off Study criteria (below).

5.5 Criteria for Removal from Study

The date and reason for the subject coming off study must be documented in the eCRF and the Operations, Biostatistics and Data Management Core must be notified according to standard reporting guidelines (see Section 7 and the Required Data and Timetable Submission form located on the PBTC-039 protocol and resources webpage).

- Subject determined to be ineligible.
- Parent, subject, or guardian withdraws consent for continued participation.
- Subject death while on study. The IRB, Study Chair and OBDMC must be notified as per Section 7.
- Subject has completed all trial-specified evaluations and follow-up.

• Subject has started another therapy or experienced disease progression (section 11.1.3).

5.5.1 Off-Study Data Submission Schedule

No data will be collected documenting treatment or reporting events or disease status that occur subsequent to the official "off study" date with the exception of adverse events with an attribution of possible, probable, or definite that occur after the "off study" date (per protocol Section 7).

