7.3 Routine Adverse Event Reporting

Adverse Events **must** be reported in routine study data submissions as outlined below:

- Any baseline (pretreatment) abnormalities observed during the initial physical examination should be recorded in the PBTC RDC database.
- Only record adverse events Grades 1 and 2 if the attribution is at least possibly related to SYLATRON. Record all adverse events Grades 3 through 4 and deaths (while on treatment or within 30 days of treatment), regardless of attribution on the electronic case report forms (PBTC RDC database).

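### The off-study data cut-off in 5.5.1 conflicts with the 30-day follow-up in 5.4.1 and the all-attribution reporting in 7.3, so unrelated-rated grade 3-4 events and deaths after progression can go unrecorded

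*Combined protocol and SAP*

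**What the plan says.** Progression ends treatment: section 5.3.2 lists "Disease progression as defined in Section 11.1.3" among the off-treatment criteria. It also ends study participation: section 5.5 lists "Subject has started another therapy or experienced disease progression (section 11.1.3" among the criteria for removal, without stating any interval.

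Section 5.4 opens with a general rule, "Patients who are off protocol therapy must be followed until an" off-study criterion is met. Its item 5.4.1 is specific to patients with progression or recurrence, who "will be followed for 30 days after the last dose of SYLATRON or until the resolution of all SYLATRON related toxicities, whichever is longer".

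Section 5.5.1 sets the data cut-off. After the official off-study date, "No data will be collected documenting treatment or reporting events or disease status", "with the exception of adverse events with an attribution of possible, probable, or definite that occur after the" off-study date, with a pointer to Section 7.

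Section 7.3, on routine reporting to the study database, says: "Record all adverse events Grades 3 through 4 and deaths (while on treatment or within 30 days of treatment), regardless of attribution".

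Section 7.2.1 requires expedited reporting of serious events whether or not they are related. Its footnote 1 brings in attribution only for serious events more than 30 days after the last administration.

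**The concern.** Sections 5.5 and 5.5.1, read literally, take a patient off study at progression and from then on admit only drug-related adverse events. Sections 5.4.1 and 7.3 require more from the same patient over the same days. A site cannot date off study at progression, apply 5.5.1, and also meet 7.3.

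At stake is secondary objective 1.2.3, the toxicity profile, which section 13.3 reports as frequency tables by stratum. Under 5.4.2, patients who stop for reasons other than progression stay in follow-up, so ascertainment in the weeks after the last dose could differ by reason for stopping. For patients who progress it would rest on the site's attribution, and with no control arm there is nothing against which to check that attribution.

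**Working it through.** The plan gives no figure on this point, so the main check sets the rules side by side for one patient: treatment stops at progression, and a grade 3 event rated unlikely occurs before day 30 after the last dose.

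| Rule | What it asks for |
|---|---|
| 5.4, general rule | Follow-up lasts until an off-study criterion is met |
| 5.5 | Progression is such a criterion; no delay is stated |
| 5.5.1 | After the off-study date, only events rated possible, probable or definite: **not collected** |
| 5.4.1 | Patient still in follow-up to day 30 or later |
| 7.3 | Grade 3, within 30 days of treatment, any attribution: **must be recorded** |

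**Does the pointer to Section 7 inside 5.5.1 resolve this?** No. It is attached to an exception worded for related events only. Section 7.2.1 restricts by attribution only beyond 30 days after the last administration, whereas 5.5.1 restricts from the off-study date, which can fall inside those 30 days.

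**Is the off-study date fixed elsewhere?** No. Nothing sets it, for a patient who progresses, at the end of 5.4.1 follow-up. Section 5.4 sends the reader to section 5.6 for the off-study criteria, but 5.6 covers concomitant medication; the criteria are in 5.5.

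**What can be lost.** Grade 3-4 events and deaths rated unlikely or unrelated, from the off-study date to day 30 after the last dose. If weekly dosing (section 5.1) runs uninterrupted until progression, the last dose is at most 7 days earlier, so the exposed window is 30 − 7 = 23 to 30 days. A second gap is smaller: the exception covers events that occur after the off-study date, which leaves unclear whether data on the resolution of a related event that began earlier are collected, although 5.4.1 requires follow-up to resolution.

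**How many patients.** Inputs are from section 13.3: 28 evaluable Stratum 1 patients, and 1-year stabilization rates of 50% (unacceptable) and 75% (desirable). Expected failures in year 1 = n × (1 − rate):

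- rate 75%: 28 × 0.25 = 7
- rate 50%: 28 × 0.50 = 14

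These bound the expected number of exposed patients from above, for two reasons. Failure also includes death (13.3) and withdrawal, loss to follow-up or a missing evaluation (13.4.1 and the note to the study calendar). And a patient who stopped earlier for another reason and progresses more than 30 days after the last dose loses nothing under 7.3. The bound covers Stratum 1 in year 1 only; later Stratum 1 progressors and all Stratum 2 progressors are additional.

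**How many events.** The documents give no rate of unrelated grade 3-4 events after progression, so this cannot be calculated.

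**The case against.** The strongest reply is that the sections can be read together. Section 5.5.1 runs from the official off-study date, and nothing says that this is the date of progression. Section 5.4.1 is the specific rule for patients who progress, 5.5 also lists completion of all required follow-up as a reason to leave, and 7.3 is a separate obligation tied to treatment, not to study status. A site that dates off study after 5.4.1 follow-up satisfies every section. Section 5.5 also refers to a data-submission timetable that is not part of these documents.

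This stands in part. Loss is conditional on how the site sets the date. A reader might infer that safety data are in fact truncated for every patient who progresses; the documents do not support that. They do support a conflict that sites can resolve in different ways, because progression is listed on its own in 5.5 as sufficient.

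A second reply is that expedited reporting catches these events. It does so for serious ones, related or not, within 30 days of the last administration, so deaths in that window still reach safety oversight. Non-serious grade 3-4 events are not covered. A reader might go further and infer that expedited reports never feed the toxicity tables. Section 13.3 does not name the tables' data source, so that cannot be asserted. What the text does show is that routine events go to the study database graded under CTCAE 4.0 (sections 7.1 and 7.3), while expedited reports use version 5.0 from April 2018, so the two sources are not directly interchangeable.

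**Conclusion.** Wrong as written: sections 5.4, 5.5, 5.5.1 and 7.3 contradict each other and should be reconciled. Where a site dates off study at progression and applies 5.5.1, unlikely- or unrelated-rated grade 3-4 events and deaths up to day 30 after the last dose can be absent from routine data. Where sites differ, capture is uneven.

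The reach is limited. Adverse events rated at least possibly related are still collected. The primary endpoints and PFS do not depend on data after progression. What is affected is objective 1.2.3 and its tables. The 7 to 14 of 28 assumes that every Stratum 1 failure in year 1 is a progression within 30 days of the last dose and that every site dates off study at progression; it counts patients exposed to the gap, not events lost.

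The same gap arises for a patient who starts another therapy within 30 days of the last dose. It would be tempting to say that 5.4.1 already requires follow-up there too, but 5.4.1 covers only progression or recurrence.

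**What to change.** Three wording changes:

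1. In 5.5, state that the off-study date for a patient who progresses is no earlier than the end of the 5.4.1 follow-up. The words *no earlier than* matter: a patient who progresses long after the last dose should not be backdated.
2. In 5.5.1, make the cut-off expressly subject to 7.2.1 and 7.3 by adding to the exception: *and all grade 3-4 adverse events and deaths within 30 days of the last dose, regardless of attribution*. This also covers patients who start another therapy within 30 days.
3. In 5.4, correct the cross-reference for the off-study criteria from 5.6 to 5.5.

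The changes use windows that the protocol already sets in 5.4.1 and 7.3. The cost is the amendment wording and slightly more data entry.

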5.6 General Concomitant Medication and Supportive Care Guidelines

The only contraindicated medications are Phenytoin, Warfarin, and Methadone, which are listed in the eligibility/exclusion criteria. Patients should be asked and should inform their healthcare providers about any OTC medications that they are taking, particularly those containing acetaminophen, in order to avoid over-dosage.

